#### **8.4 Study intervention:**

There are no known risks associated with the AQI.

### **9. INFORMED CONSENT:**

There is one consent form for both the parent participant and the child participant. Informed consent and child assent will be obtained after thorough discussion of the potential risks and benefits.

### **10. ADVERSE EVENTS:**

#### **10.1 Adverse events**

The risk for adverse events related to the study intervention are minimal. An adverse event will be defined as an unexpected accident, experience, or outcome that is unexpected (in terms of nature, severity, or frequency), is related or possibly related to the subject's participation in the research, and places subjects or others at a greater harm (including physical, psychological, economic, or social harm) than was previously known or recognized. Such events will be recorded as per 45 CFR part 46. Unexpected adverse events of moderate severity will be reported to the IRB within 10 working days of the investigator learning of the event.

As asthma is a chronic lung disease with waxing and waning impairment and risk, asthma exacerbations (both severe & moderate) and loss of control are not unexpected. We will consider an increased severity or frequency of such events as adverse events, although these will not meet the definition required for reporting to IRB as these such events are not anticipated to be related or possibly related to the research.

Specific examples of these are below. While these will not require reporting to the IRB, they will be captured as adverse events and safety procedures will be implemented as below:

1. If a participant has more than 3 severe asthma exacerbations during the study
2. If a participant has 3 consecutive ACT or C-ACT scores  $\leq 19$ .
3. If a participant has an FEV1  $< 80\%$  at either V1 or V7

These events will be recorded, parent or guardian/participant will be notified of possible poorly controlled asthma and will be encouraged to follow up with managing asthma specialist. With parental permission, PI or RC will reach out to managing asthma specialist to alert to concerns.

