## 10.2 Serious Adverse Event

A serious adverse event will be defined as an event that is fatal, life-threatening, inpatient hospitalization or prolongation of hospitalization, a persistent or significant incapacity or substantial disruption of the ability to conduct normal life functions.

As we anticipate learning of such events (e.g. hospitalization for asthma exacerbation) retrospectively (thru questionnaire) we will inquire about whether the participant has been seen by managing asthma specialist since event. If the answer is no, we will encourage family/participant to contact asthma specialist and with permission, PI or RC will alert managing asthma specialist.

Serious adverse events will be reported to the IRB within 24 hours of learning of any unexpected serious adverse event associated with the research intervention.

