## STATISTICAL PLAN:

Statistical Analysis: Data will be analyzed using SAS (SAS 9.4, Cary, N.C.). Baseline statistics per treatment group will be obtained. Bivariate analysis of covariates (age, sex, race/ethnicity, asthma severity, phenotype (i.e. atopic), socioeconomic status (SES), exposure to primary or secondary tobacco smoke, FeNO, use of controller medication, etc) between groups will be conducted using student t-test or Wilcoxon rank sum and Fisher's exact or Chi-square (where appropriate and based on distribution). Variables with significant differences between groups ( $P<0.05$ ) will be considered for inclusion in multivariate model selection. The effects of physical activity on the outcomes will be compared between groups. Baseline knowledge and usage of AQI will be assessed. Adherence to AQI will also be assessed and compared between groups, with potential stratification by AQI usage. Additionally, differences in weight and BMI will be assessed to evaluate if adherence to AQI promotes sedentarism and leads to increased weight gain. We will evaluate our outcomes (Aims 2 and 3) in three ways. First, we will evaluate the average difference (overall mean) between groups for our primary outcomes using T test or chi-square (where appropriate). Additionally, we will test the average mean difference between each treatment group by multivariate regression (linear for PAQLQ and ACT or CACT, and/or Poisson or logistic regression for mean asthma exacerbations depending on distribution) to allow for covariate adjustment. Second, we will use paired t-tests (or matched Wilcoxon signed-rank) to evaluate the within group effects (6 month mean – baseline) for each primary outcome. Third, to assess the effects over time in our intervention study (correlated repeat measures data), we anticipate analyzing our primary outcomes by generalized linear mixed models (GLMM). For these models, we will first evaluate the distribution of our primary outcome and determine the most appropriate link (e.g. for severe asthma exacerbations: logistic link if there are overall a high proportion of participants with none, or Poisson link if more consistent with count data). A stepwise approach will be used to build all multivariable models. All final models will include age, sex, race/ethnicity, SES, and tobacco smoke exposure. Additionally, the above outcomes will be stratified by age group (8-12y, 13-17y) to determine if the effects are greater in older children for whom the AQI recommendations may be better self-incorporated into outdoor physical activities, vs the younger group who will likely be more reliant on parental checking and activity modification.

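### Section 10.1 decides in advance, as a class, that increased exacerbations are not related to the research, so no required step assesses or reports an excess in the AQI arm while the trial runs

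*Combined protocol and SAP*

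**What the plan says.** Section 10.1 defines an adverse event by three conditions that must all be met: it is unexpected, it "is related or possibly related to the subject's participation in the research", and it exposes people to more harm than was previously recognised.

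The section then turns to the disease under study. It states that "asthma exacerbations (both severe & moderate) and loss of control are not unexpected". An increase in their severity or frequency is to count as an adverse event, but "these will not meet the definition required for reporting to IRB". The reason it gives concerns the whole class: "as these such events are not anticipated to be related or possibly related to the research". Three examples follow: repeated severe exacerbations, a run of low ACT or C-ACT scores, and a low FEV1 at the first or last visit. Of these it says: "While these will not require reporting to the IRB, they will be captured as adverse events". The prescribed action is to tell the family and, with permission, the asthma specialist.

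Section 10.2 counts "inpatient hospitalization or prolongation of hospitalization" as serious. The 24-hour IRB report covers only serious events that are both unexpected and associated with the intervention. Section 14 answers excess asthma events with contact to the family and, with permission, the specialist.

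On the risk of the intervention itself, section 8.4 says: "There are no known risks associated with the AQI". Section 2.5 and the Statistical Plan nevertheless measure weight and BMI, the latter "to evaluate if adherence to AQI promotes sedentarism and leads to increased weight gain".

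**The concern.** The hypothesis in section 2.1 is that the intervention alters exacerbation frequency, and the power calculation is two-tailed. A plan that treats an outcome as modifiable by the intervention for efficacy should not settle beforehand, for safety, that a change in the same outcome is unrelated. Relatedness is a judgement on an event after it happens. Here it is made once, for a whole class of events, before any child is enrolled.

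At stake is whether anyone is obliged to ask, during the trial, if a child's severe exacerbation or admission might have to do with the arm the child is in. The participants are children, and the arms differ in written advice about outdoor activity. Section 8.4 raises the same issue on a smaller scale: a possible harm that the plan thinks worth measuring does not appear in the risk section.

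**Working it through.** The plan gives no figure for this point, so the main check follows one event through the rules: an asthma hospitalisation of a child in the AQI arm.

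1. **Adverse event under the 10.1 definition?** The event must be unexpected and at least possibly related. The same section classes exacerbations as not unexpected and does not anticipate relatedness. On the definition the answer is no. If the event is instead seen as an increase in severity or frequency, 10.1 calls it an adverse event anyway. The definition and its application cannot both stand. The FEV1 example shows the same strain: it includes a first-visit value, which section 11.2 lists before the AQI education.
2. **Reported under 10.1?** The 10-working-day route needs an unexpected event, and increased exacerbations are expressly taken out of IRB reporting.
3. **Serious under 10.2?** Yes. Reported within 24 hours? Only if unexpected and associated with the intervention. Section 10.1 has already leaned against both, so most likely not. The stated action is to ask whether the asthma specialist has seen the child.
4. **Picked up under section 14?** The family and specialist may be contacted. Neither a comparison by arm nor an IRB notice is specified.

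At no step is anyone required to judge relatedness for this child.

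**Sedentarism and weight.** Section 8.4 states no known risk. Section 2.5 and the Statistical Plan treat reduced activity and weight gain as possible consequences of adherence, section 2 aims not to discourage activity, and Figure 5 advises less or relocated outdoor exertion at the higher AQI categories. This harm is not among the events excluded from IRB reporting, but no threshold or route is named for it.

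**Triggers.** For severe exacerbations, 10.1 acts at more than 3 and 11.3 at 3. For ACT or C-ACT scores of 19 or less, 10.1 requires 3 in a row, while the 11.3 wording is garbled and can be read as more than 3.

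**Illustration of the severe-exacerbation trigger.** Inputs: 20 children per arm (Power calculations); the Poisson law and its mean λ per child over follow-up are assumptions, because the documents give no rate.

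- More than 3: p = 1 − e^(−λ)(1 + λ + λ²/2 + λ³/6)
- At least 3: p = 1 − e^(−λ)(1 + λ + λ²/2)
- Any of 20 children: 1 − (1 − p)^20

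For λ = 0.5 and more than 3: p = 1 − 0.6065 × 1.6458 = 0.00175, and 1 − (1 − 0.00175)^20 = 3.4%.

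| Assumed λ | p, more than 3 | Any of 20, more than 3 (10.1) | Any of 20, at least 3 (11.3) |
|---|---|---|---|
| 0.25 | 0.00013 | 0.3% | 4.2% |
| 0.5 | 0.00175 | 3.4% | 25% |
| 1.0 | 0.0190 | 32% | 81% |
| 1.5 | 0.0656 | 74% | 99% |

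Under these assumptions, a doubling from 0.25 to 0.5 would rarely trip the 10.1 trigger. When tripped, it leads to the family and specialist, not to the IRB. The last two columns show that the mismatch between 10.1 and 11.3 is not trivial.

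**The case against.** A reader might infer that a worse AQI arm could never reach the IRB. The documents do not say that. Section 10.1 speaks of what is not anticipated, which is weaker than ruling relatedness out. Section 10.2 keeps a 24-hour route for an unexpected serious event linked to the intervention, and weight gain is left within the general 10.1 route.

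A reader might also infer that harm could not be seen while the trial runs. That is not supported either. Exacerbations, ACT or C-ACT scores and physical activity are collected at every follow-up visit, the trial is unblinded, and section 14 provides for close monitoring of the data. Nor is a single hospitalisation lost: 10.2 uses it as its own example and gives follow-up steps. What is missing is an obligation to assess and report, not the ability to notice.

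Three further objections carry weight. The items in 10.1 are examples that serve individual follow-up, so it is unfair to judge them as detectors of a difference between arms. The Poisson means are unsourced. A two-tailed test is a convention and does not by itself admit harm; the stated hypothesis is directional. The argument does not need that inference: it is enough that exacerbations are an outcome the intervention is meant to influence.

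On 8.4, it can fairly be said that no known risk is compatible with studying an unproven one, that both arms receive the same AQI education, and that the handout encourages activity. This makes the fault one of omission rather than contradiction.

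**Conclusion.** The point stands as a defect of rule and wording. Section 10.1 prejudges relatedness for an outcome the trial tests, contradicts its own definition of an adverse event, and expressly keeps increased exacerbations from the IRB. With 10.2 and 14 read alongside, the plan has no required route by which an excess of exacerbations in the AQI arm would be assessed for relatedness or reported during the trial. That an ordinary asthma hospitalisation would be filtered out is an inference from reading 10.1 and 10.2 together; neither section says so outright.

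The conclusion rests on the text and not on the Poisson figures, which only illustrate one trigger under assumed rates. For a 40-child, low-risk pilot this is something the sponsor should correct, not a reason to doubt the trial. The consent text was not available, so nothing is concluded about what families are told.

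**What to change.** - **10.1:** delete the class-wide statement on relatedness. Define an adverse event without requiring relatedness, so that every 10.2 event is one. Keep the three-part test (unexpected, related or possibly related, greater harm) solely as the criterion for IRB reporting. Have the investigator record a relatedness judgement for each severe exacerbation and each hospitalisation.
- **8.4:** replace the statement of no known risks with text that names reduced activity and weight gain as possible risks under study, in line with section 2.5 and the Statistical Plan. Check that the consent text agrees.
- **10.1 and 11.3:** reconcile the severe-exacerbation trigger and the two wordings of the ACT or C-ACT trigger. Which version is intended is for the sponsor to say.

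A monthly by-arm review by an unblinded investigator is not asked for. Its value in a trial of this size is debatable, and the monthly meetings in section 11.6 are for deviation reports.

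The cost is protocol wording, possibly consent wording, and slightly more event paperwork on events that are already asked about monthly.

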## 10.2 Serious Adverse Event

A serious adverse event will be defined as an event that is fatal, life-threatening, inpatient hospitalization or prolongation of hospitalization, a persistent or significant incapacity or substantial disruption of the ability to conduct normal life functions.

As we anticipate learning of such events (e.g. hospitalization for asthma exacerbation) retrospectively (thru questionnaire) we will inquire about whether the participant has been seen by managing asthma specialist since event. If the answer is no, we will encourage family/participant to contact asthma specialist and with permission, PI or RC will alert managing asthma specialist.

Serious adverse events will be reported to the IRB within 24 hours of learning of any unexpected serious adverse event associated with the research intervention.

## 11. CLINICAL MANAGEMENT AND DATA COLLECTION:

Table 2: Summary of Study Protocol

VISIT	LOCATION	TIMING	QUESTIONNAIRE	MEASURES	SPECIMENS
V1	In-person, PCTRC	Start	AQI intake*, Intake, PA, ACT or CACT, PAQLQ, tobacco intake	Spirometry, FeNO, ht, wt	NEC, urine
V2	Telephone	W4, 4 wks post V3 (+/- 7d)	sRQ, AQI_f/u, PA, ACT or CACT.	-	-
V3	Telephone	W8, 4 wks post V3 (+/- 7d)	sRQ, AQI_f/u, PA, ACT or CACT.,	-	-
V4	Telephone	W12, 4 wks post V3 (+/- 7d)	sRQ, AQI_f/u, PA, ACT or CACT.	-	-
V5	Telephone	W16, 4 wks post V3 (+/- 7d)	sRQ, AQI_f/u, PA, ACT or CACT.	-	-
V6	Telephone	W20, 4 wks post V3 (+/- 7d)	sRQ, AQI_f/u, PA, ACT or CACT.	-	-
7V	In-person, PCTRC	W24, 4 wks post V3 (+/- 7d)	sRQ, AQI_f/u, PA, ACT or CACT.	Spirometry, FeNO, ht, wt	NEC, urine

Intake questionnaire (completed by parent); AQI intake- includes parent portion (completed by parent) + AQI follow up (completed by participant); PA=physical activity (parent and/or participant), ACT=asthma control test ages 12 and older (completed by participant); CACT=childhood asthma control test for ages 8-11 (completed by parent and participant); PAQLQ(s)-pediatric asthma quality of life questionnaire (completed by participant); participant tobacco intake form (completed by participant); sRQ= shortened respiratory questionnaire (completed by parent); AQI\_f/u=AQI follow up questionnaire (completed by participant).

Ht=height, wt=weight, NEC=nasal epithelial cells

\*AQI intake form should be completed prior to AQI education/intervention.

## **11.1 Recruitment**

Recruitment will occur at UPMC Children's Hospital of Pittsburgh Pediatric Pulmonology and from Pediatric Asthma Registry. A referral log will be used to track the age and gender of every child whose family is approached about the study but declines or who is not eligible because of lack of home internet or smart phone access. The research coordinator will determine eligibility criteria (as much is possible) prior to reaching out to family about study.

## **11.2 Eligibility and Randomization (Visit 1)**

Once the family and participant have indicated willingness to participate and have scheduled a V1, the research coordinator will notify PI. PI will review medical record (granted permission by Asthma Registry patients and allowable access as part of regular duties) to confirm asthma controller medications. PI will prepare AAP for research coordinators to distribute. In the event of a discrepancy between parental reported controller medication and medical record medication, the PI will reach out (with participant parent permission) to healthcare provider managing asthma to confirm asthma controller medications.

After informed consent has been obtained, participant's will be randomized 1:1 by age group. The RC assign random group at time of intervention. Eligibility for lung function tests and/or NEC will be assessed prior to study procedures. Questionnaires will be administered, height and weight will be obtained, lung function tests will be obtained (if eligible), specimens will be collected (if applicable), and AQI education will be provided. For the intervention group only, the AAP containing the AQI information will be provided. The intervention group will demonstrate ability to navigate to either airnow website or airnow app on smart phone. For the control group, an AAP will be provided (containing no AQI information) Both the participants, parents, and research coordinator will know randomization assignment. V1 should not be done if child participant has been sick with respiratory infection in prior 7 days or currently has respiratory symptoms.

If a participant's spirometry demonstrates an FEV1 <80%, the family and participant's managing asthma healthcare provider will be notified. Per family permission, spirometry will be shared with managing asthma healthcare provider. If a participant's FeNO is above 20ppb, with family permission, FeNO will be shared with managing asthma healthcare provider.

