### 2.1 Hypothesis and Specific Aims

We hypothesize that the addition of the AQI to AAP will (A) reduce asthma exacerbations, and (B) improve symptom control & quality of life in children with asthma. To test these hypotheses, in this study we will pursue the following specific aims:

- Aim 1: To recruit a pilot cohort of 40 children with asthma. For proof of concept, we will recruit 40 children with asthma from Children's Hospital of Pittsburgh, the only children's hospital serving southwest Pennsylvania (metropolitan area >2.6 million people). Baseline knowledge about the AQI including familiarity, usage, and prior healthcare provider discussion will be assessed.

- Aim 2: To evaluate if the addition of the AQI to AAP reduces asthma exacerbations in a pilot study of children. Participating children (Aim 1) will be randomized to one of two groups. All participants/caregivers will receive an AAP and verbal AQI education. The intervention group will additionally demonstrate the ability to check the AQI, and AQI recommendations will be incorporated onto their written AAP. Children will be followed monthly for 6 months to evaluate adherence to AQI recommendations and assess the frequency of asthma exacerbations, defined per ATS guidelines. Other known factors contributing to asthma exacerbations, such as asthma severity, viral illnesses, allergic triggers will also be monitored.
- Aim 3: To examine whether the addition of the AQI to AAP improves asthma symptom control and quality of life in a pilot study of children. Asthma symptom control will be measured in participating children monthly, and quality of life will be assessed before randomization and at 6 months. Symptom control and quality of life will be evaluated within (before/after intervention) and between groups.

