## 2.3 Questionnaires

7 questionnaires will be administered to the parents and children of study participants (see Figure 4). (1) Intake Questionnaire: this is a respiratory/general health questionnaire used by the [REDACTED] Study. (2) Tobacco Questionnaire- this is a short questionnaire from questions used on the National Youth Tobacco Survey. (3) AQI intake & follow up: Intake: there are no existing questionnaires evaluating what parents know about the AQI as pertains to their children with asthma. This questionnaire contains questions from NHANES and BRFSS with modifications. The AQI intake has a section to be completed by the parent to understand the parent's knowledge and practices regarding the AQI. The

intake questionnaire additionally contains a section for the child to complete, which is the AQI follow up questionnaire. The follow up questionnaire was developed by the PI to assess usage of the AQI. **(4)** Asthma Control Test (ACT) and Childhood Asthma Control Test (C-ACT) are validated questionnaires to assess asthma control in the last 4 weeks. **(5)** Pediatric Asthma Quality of Life Questionnaire (PAQLQ(S)) is validated questionnaire that will be interviewer-administered. **(6)** Physical activity questionnaire contains modified questions from NHANES and The Physical Activity Questionnaire for older children and adolescents. **(7)** Shortened respiratory questionnaire (sRHQ): this is a short questionnaire that has been modified from the [REDACTED] study. It is designed to capture asthma exacerbations.

The order of the questionnaires is important. The AQI intake form will be completed by the parent/guardian and the child participant prior to AQI education/intervention.

**2.4 Lung Function Tests:** Spirometry and fractional exhaled nitric oxide (FeNO) will be obtained at entrance and exit visit as secondary measures of control (e.g. forced vital capacity (FVC), forced expiratory volume in 1 sec (FEV1), and FEV1/FVC).

**2.5 Anthropometric measures:** Height and weight will be obtained at the baseline and exit visit, to assess if adherence to AQI potentially alters weight/BMI by increased sedentarism.

**2.6 Urine collection:** as an ancillary to this study, will collect urine for cotinine measurement (nicotine metabolites) and store.

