### **5.1 Inclusion Criteria:**

#### Child participant:

1. Physician diagnosed persistent asthma (mild, moderate, or severe).
2. Aged 8-17 years old (at time of consent)
3. Family home internet access or smartphone access + willingness to download AirNow app on phone

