**8.1b Spirometry:** The risks of spirometry are minimal and include temporary lightheadedness from repeated spirometry maneuvers and there is a small risk (rare) of wheezing and shortness of breath and increased cough when performing spirometry. If the participant has had a pneumothorax (a.k.a collapsed lung, air leak), open thoracic surgery (a.k.a open chest surgery), myocardial infarction (a.k.a heart attack), or hemoptysis (a.k.a coughing up blood) in the last 2 months they should not undergo spirometry.

**8.1c Fractional Exhaled Nitric Oxide (FeNO):** The risks of FeNO are similar to spirometry in that they are minimal may include temporary lightheadedness. If the participant has had a pneumothorax (a.k.a collapsed lung, air leak), open thoracic surgery (a.k.a open chest surgery), myocardial infarction (a.k.a heart attack), or hemoptysis (a.k.a coughing up blood) in the last 2 months they should not undergo FeNO.

**8.1d Nasal epithelial collection:** The main risk of the nasal sample is discomfort and nose bleeding. Additional risks include watery eyes and sneezing. There is also the rare possibility of a tear at the brushing site and infection from this procedure. We will place a small amount of lidocaine (~1cc) into the participants nose to reduce discomfort. Lidocaine will not be injected with a needle (no needles will be used). Lidocaine sometimes cause an unpleasant taste in the mouth and may cause temporary redness, stinging, and swelling at the application

site. If the participant has a bleeding disorder (coagulopathy) they should not undergo nasal cell collection.

**8.1e Urine collection:** the risks of urine collection are minimal and may include discomfort with providing a sample.

**8.1f Measures of height and weight:** possible participant discomfort with having weight obtained. The risks are minimal.

**8.2 Break of confidentiality:** participant data will be identified by a unique study number assigned to each child. The unique study number will be used as identification and not participant identifying information (ex. first name, last name, DOB) will be kept with research information. The link between study ID and participant will be kept in a secure and locked location.

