## **11.4 Exit visit (Visit 7)**

Visit 7 will be conducted in person. Eligibility for lung function tests and/or NEC will be assessed prior to study procedures. Questionnaires will be administered, height and weight will be obtained, lung function tests will be obtained (if eligible), and specimens will be collected (if applicable).

If a participant's spirometry demonstrates an FEV1 <80%, the family and participant's managing asthma healthcare provider will be notified. Per family permission, spirometry will be shared with managing asthma healthcare provider. If a participant's FeNO is above 20ppb, with family permission, FeNO will be shared with managing asthma healthcare provider.

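### Visit 1 is withheld during respiratory illness but Visit 7 is not, so within-arm change in spirometry and FeNO compares a screened-well baseline with an unscreened exit

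*Combined protocol and SAP*

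**What the plan says.** **Baseline.** Section 11.2 (Visit 1) states: "V1 should not be done if child participant has been sick with respiratory infection in prior 7 days or currently has respiratory symptoms". It does not say that the visit is then rebooked, but that is the natural reading.

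**Exit.** Section 11.4 opens: "Visit 7 will be conducted in person. Eligibility for lung function tests and/or NEC will be assessed prior to study procedures". It sets no illness or symptom condition. The test criteria are in sections 8.1b to 8.1d. For spirometry, 8.1b begins "If the participant has had a pneumothorax (a.k.a collapsed lung, air leak), open thoracic surgery" and continues with myocardial infarction and hemoptysis, all within the last two months. FeNO has the same list, and nasal sampling adds bleeding disorder. Respiratory infection appears in none of them. Table 2 times Visit 7 as "W24, 4 wks post V3 (+/- 7d", that is, week 24 with a 7-day window either side, and makes no provision for deferral. (The reference to Visit 3 in that cell is a separate matter.)

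**Use of the two visits.** Section 2.4 takes spirometry and FeNO at entry and exit only, as secondary measures of control. For Aim 3, section 2.1 says: "Symptom control and quality of life will be evaluated within (before/after intervention) and between groups". The Statistical Plan uses paired tests to "evaluate the within group effects (6 month mean – baseline) for each primary outcome". Section 2.3 says that ACT and C-ACT "are validated questionnaires to assess asthma control in the last 4 weeks".

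**Population.** Section 5.1 admits "Physician diagnosed persistent asthma (mild, moderate, or severe".

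**The concern.** A before/after difference can be read as change over the study only if both measurements are taken under the same conditions. Here the first is taken on a day when the child has no recent infection and no symptoms, and the second on whatever day falls in the window. Even with no true change, the exit mean would then include some ill-day readings that the baseline mean excludes by rule.

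Spirometry and FeNO are the most exposed. They reflect the child's state on the day, and no intermediate visit could offset one bad reading. For FEV1 the likely direction is apparent worsening or masked improvement; for FeNO the documents give no basis for a direction. Illness at exit also widens the spread of exit values in both arms, which matters somewhat with 20 children per arm. ACT and C-ACT face the same asymmetry in weaker form.

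**Working it through.** **1. Conditions side by side.**

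| | Visit 1 (11.2) | Visits 2-6 (11.3) | Visit 7 (11.4) |
|---|---|---|---|
| Infection in prior 7 days | visit not done | no condition | no condition |
| Current respiratory symptoms | visit not done | no condition | no condition |
| Spirometry, FeNO | yes | no | yes |
| ACT or C-ACT | yes | yes | yes |

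The Statistical Plan does not say whether its 6-month mean is the month-6 score or an average over follow-up. The asymmetry holds either way, because no follow-up visit has an illness rule. Section 2.1 says viral illnesses will be monitored, but the Statistical Plan gives illness at the visit no role in the paired comparison.

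**2. The plan's own within-group power.** The stated figures are at least 90% power at 0.76 and at least 80% at 0.66, with 20 per group and two-sided alpha 0.05. No SD is given. Take a paired t-test with df = 19, SD of the change = 1 and noncentrality d x sqrt(20):

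- d = 0.76: 0.76 x 4.472 = 3.40, power 89.7%
- d = 0.66: 0.66 x 4.472 = 2.95, power 80.0%

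Both reproduce to rounding, so the plan's differences are in units of the SD of the change. They do not allow for illness.

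**3. Size of the shift.** If a share q of children is ill or symptomatic at an unscreened visit, and their reading is then lower by D on average, the spurious mean change is -q x D. The documents give neither q nor D, so every value below is an assumption.

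- FEV1, q = 15-30%, D = 5-10 points of % predicted: 0.15 x 5 = 0.75 to 0.30 x 10 = 3.0 points downward.
- ACT, same q, D = 3 points: 0.15 x 3 = 0.45 to 0.30 x 3 = 0.9 points. Against the 2-3 point clinical difference in the power paragraph, this is 0.45/3 = 15% to 0.9/2 = 45%. It is probably high for a brief illness, which occupies only part of a four-week recall period.

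**4. Effect on a paired test, in SD units.** Assume q = 10-30% and D = 0.5-1.5 SD of the change, with that SD held at 1.

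| q x D | Shift (SD) | Rejection rate, no true change | Power, true improvement 0.66 SD |
|---|---|---|---|
| none | 0 | 5% | 80.0% |
| 0.10 x 0.5 | 0.05 | 5.5% | 73.5% |
| 0.20 x 1.0 | 0.20 | 13.6% | 49.7% |
| 0.30 x 1.5 | 0.45 | 48.0% | 14.5% |

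The spread shows that the answer depends wholly on the assumptions.

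**5. Noise at exit.** If D is constant among ill children and unrelated to their usual level, illness adds variance q(1 - q)D^2 to the exit reading. For FEV1 this is 0.15 x 0.85 x 25 = 3.2 to 0.30 x 0.70 x 100 = 21 squared points.

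**6. Between arms.** The same rules apply to both arms, so with equal q and D the shift -q x D cancels from the difference in means. If the intervention changed q or D, that difference would be part of its effect.

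**The case against.** The strongest reply is that the trial's question is the randomized contrast and that this contrast is untouched. The paired tests are the second of three analyses. A single-arm change is already open to season and to the action plan and AQI education that both arms receive. The paired tests are also written for the primary outcomes, and no paired analysis of FEV1 or FeNO is specified. All of this stands, and it is why the point is minor. It does not make the two lung function visits comparable.

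A reader might infer more than the documents support:

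- **That the between-arm effect is biased.** It is not (step 6).
- **That children with daily symptoms can never have Visit 1.** Symptoms are not an exclusion in section 5.2, and beside the infection clause the wording can be read as acute illness. The clause does sit awkwardly with section 5.1, but that is a matter of wording to reconcile.
- **That baseline control scores are pushed to a ceiling.** The rule looks at the past 7 days and the day itself, while ACT and C-ACT cover four weeks. Sections 10.1 and 11.2 expect impaired children, with actions for FEV1 below 80% at Visit 1.
- **That the paired test has a 48% false-positive rate.** That is the extreme corner of assumed ranges.
- **That Visit 7 should carry the whole Visit 1 rule.** Symptoms at exit are part of the outcome, and screening them out would remove what the trial sets out to measure.

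The Visit 7 window allows some rebooking, but nothing asks for it.

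**Conclusion.** The concern holds in a narrow form, and its severity is minor. The visit conditions differ in the text, and no other section closes the gap. Spirometry and FeNO are the measures mainly affected. Their within-arm change may be shifted, for FEV1 probably downward, and their exit values are noisier. The before/after change in ACT and C-ACT is affected less. PAQLQ is left aside, because neither visit table lists it at Visit 7 and that has to be settled first.

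The documents do not fix the size. The 0.75-3.0 FEV1 points rest on an assumed 15-30% of children ill or symptomatic at exit and an assumed 5-10 point decrement. That share pools infection with symptoms, so it overstates what an infection condition alone would remove.

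**What to change.** 1. **Section 11.4.** Apply the Visit 1 infection condition to Visit 7 spirometry and FeNO, and rebook only these tests within a short, stated extension of the 7-day window. Keep ACT or C-ACT and the shortened respiratory questionnaire on their planned date, so that outcome data are neither delayed nor lost.
2. **Visit forms and Statistical Plan.** Record recent respiratory infection at Visits 1 and 7. As a sensitivity analysis, repeat the Visit 1 to Visit 7 analyses, including ACT and C-ACT, without Visit 7 visits held during infection. It should remain a sensitivity analysis, because infection at exit arises after randomization.
3. **Symptom clause.** Do not apply it at Visit 7. Because that leaves part of the asymmetry in place, above all for ACT and C-ACT, state in the Statistical Plan that within-arm change is descriptive. Reconcile the wording of the clause in 11.2 with the inclusion of persistent asthma in 5.1.

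The cost is a few sentences and one form item. The downside is an occasional rebooked lung function test among 40 children and a slightly wider Visit 7 window for those tests.
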